6. SPECIFIC AIMS

The ultimate objective of the proposed line of research is to determine if cryoanalgesia is an effective treatment for pain associated with rib fractures; and, if this analgesic modality improves pulmonary mechanics measured with incentive spirometry.

Specific Aim 1: To determine if, compared with current and customary analgesia for rib fracture(s), intercostal nerve cryoneurolysis improves maximum inspiratory volume.

Hypothesis 1a: The maximum inspired volume will be significantly *increased* on the day following the procedure [primary endpoint] as well as at other time points following the procedure [secondary end points] with intercostal cryoanalgesia as compared single-injection local anesthetic-based intercostal nerve blocks [measured with an incentive spirometer].

Hypothesis 1b: The maximum inspired volume as a percentage of the baseline will be significantly *increased* on the day following the procedure [secondary endpoint of greatest interest], as well as at other time points following the procedure [secondary end points] with intercostal cryoanalgesia as compared with single-injection local anesthetic-based intercostal nerve blocks [measured with an incentive spirometer].

Specific Aim 2: To determine if, compared with current and customary analgesia, intercostal nerve cryoneurolysis decreases the pain associated with rib fracture(s).

Hypothesis 2a: The severity of rib fracture pain at rest will be significantly decreased within the 12 months following the procedure with intercostal cryoneurolysis as compared with subjects receiving single-injection local anesthetic-based intercostal nerve blocks [measured using the Numeric Rating Scale for pain].

Hypothesis 2b: The severity of rib fracture pain when using the spirometer or coughing will be significantly decreased within the 12 months following the procedure with intercostal cryoneurolysis as compared with subjects receiving single-injection local anesthetic-based intercostal nerve blocks [measured using the Numeric Rating Scale for pain].

Hypothesis 2c: The incidence of chronic pain will be significantly decreased 6 and 12 months following a rib fracture with intercostal cryoneurolysis as compared with subjects receiving single-injection local anesthetic-based intercostal nerve blocks [measured using the Numeric Rating Scale for pain].

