But, assuming a normal distribution, the interquartile range is approximately 1.35 standard deviations (SDs). Therefore an interquartile range of 250-50 = 200 mL (Hernandez et al. 2019) corresponds to, approximately, an SD of $200/1.35 = 148$ mL. Assuming this SD of 148 mL, a sample size of n=7 per group provides 80% power to detect a group difference of d=250 mL per group with two sided Type 1 Error 5%. To allow for a larger-than-anticipated SD, we will enroll 10 subjects per group with an evaluable primary outcome measure (n=20 for both groups combined). Accounting for drop-outs, we request a maximum enrollment of 30 subjects.

"Continuous data will be summarized with mean, SDs, medians, quartiles, and ranges; and displayed with box-and-whisker plots by group and in aggregate. Key baseline characteristics will be

tested between groups using two-sample t-tests, and summarized with Cohen's D, for continuous measures; and Fisher's Exact test for categorical variables. The primary outcome is maximum incentive spirometry volume (ISV) measured in mL on POD 1. The group difference will be tested using Welch's two-sample test. Secondary outcomes will also be tested with the two-sample t-test. No multiplicity adjustments will be applied for these secondary outcomes. The Wilcoxon signed-rank test will be used as a sensitivity analysis. Secondary analyses will include a Mixed Model of Repeated Measures with fixed-effects for time, time-by-group, unilateral vs bilateral, and the number of fractures. The model will treat time as a categorical variable and will assume a compound symmetric correlation and heterogeneous variance with respect to time. The estimated mean difference between groups at the final scheduled timepoint will be the parameter of interest and will be tested using Kenward-Roger degrees of freedom. Out-comes only measured at baseline and a single follow-up timepoint will be analyses with Analysis of Covariance (ANCOVA). The dependent variable will be change from baseline, and covariates will include group, baseline outcome, unilateral vs bilateral, and the number of fractures. Missing data is not expected due to the short follow-up in this study. However, if missing data issues arise, we will use multiple imputation which is robust to covariate-dependent Missing at Random, and tipping point analyses under various Missing Not at Random assumptions."

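### The t-test rule for secondary outcomes also covers the yes/no incidence of chronic pain, where its error modestly exceeds 5% at some attainable arm sizes; one exact test should be named instead

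*Combined protocol and SAP*

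**What the plan says.** Section 9 (Statistical Analysis) assigns Welch's test to the primary outcome and then says "Secondary outcomes will also be tested with the two-sample t-test". It does not separate continuous from binary outcomes, and does not say whether the secondary t-test is pooled or Welch.

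Section 6, Hypothesis 2c, reads "The incidence of chronic pain will be significantly decreased 6 and 12 months following a rib fracture". Hypothesis 2d covers the severity of chronic pain separately, so 2c is a comparison of proportions and not of mean scores. No cut-off on the Numeric Rating Scale (NRS) is given for counting a subject as having chronic pain.

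A test by data type does appear in section 9: Fisher's "Exact test for categorical variables". It belongs to the sentence that begins "Key baseline characteristics will be", so it governs baseline comparisons only.

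The other named analyses do not supply a test for a proportion. "The Wilcoxon signed-rank test will be used as a sensitivity analysis" refers to a paired or one-sample method, the mixed model targets a mean difference, and the ANCOVA models change from baseline.

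**The concern.** A t-test on 0/1 data in small groups is only approximate. Its true type I error depends on the arm sizes and on the underlying rate, and can fall on either side of 5%. It returns no p-value when neither arm has any variation. An analyst who noticed this could switch to an exact test, but that would depart from the written rule, and the choice would be made with the data in view. At stake is whether a lower incidence of chronic pain is declared significant, a clinically weighty claim with no multiplicity adjustment behind it.

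**Working it through.** **Inputs.** The two-sided 5% level is stated for the primary outcome ("two sided Type 1 Error 5" per cent) and taken here to apply to secondary outcomes. Section 9 plans 10 subjects per group who can be evaluated for the primary outcome, which is measured on day 1, and allows at most 30 enrolled (about 15 per group at equal allocation). Retention at 6 and 12 months and the incidence of chronic pain are not stated, so the arm sizes and rates below are assumed ranges.

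**The plan's own figure.** The documents give no calculation for the binary outcome. The primary calculation, "Assuming this SD of 148 mL, a sample size of n=7 per group provides 80% power" for a 250 mL difference, reproduces: noncentral-t power is 82.6% at 7 per group and 75.1% at 6. It has no bearing on Hypothesis 2c.

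**Method.** For arms of n and m with a common true rate p, the true error is the sum, over all tables (x, y) that the test rejects, of Bin(x; n, p) × Bin(y; m, p). The maximum is taken over p. Tables with no variation in either arm are not counted as rejections. On 0/1 data with x events in n, the mean is x/n and the sample variance is n(x/n)(1 − x/n)/(n − 1).

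**8 v 8 by hand.**
- 2 v 6: means 0.25 and 0.75; each variance 8 × 0.25 × 0.75/7 = 0.214; SE = √(2 × 0.214/8) = 0.231; t = 0.5/0.231 = 2.16 on 14 df; p = 0.049.
- 1 v 5: variances 0.125 and 0.268; SE = √(0.393/8) = 0.222; t = 2.26; Welch p = 0.043.
- 0 v 4: variances 0 and 0.286; SE = 0.189; t = 2.65 on 7 df; p = 0.033.
- 0 v 3: variances 0 and 0.268; SE = 0.183; t = 2.05 on 7 df; p = 0.080, not rejected.

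The test therefore rejects when the counts differ by 4 or more. At p = 0.5, X − Y + 8 is Bin(16, 0.5), so the error is 2 × (1820 + 560 + 120 + 16 + 1)/65536 = 5034/65536 = 7.7%. Leaving out the two 0-v-8 tables changes nothing at this precision.

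**10 v 10 by hand.** The test rejects differences of 5 or more, plus 0 v 4, 6 v 10 and their mirrors. At p = 0.5 the error is [2 × (15504 + 4845 + 1140 + 190 + 20 + 1) + 4 × 210]/1048576 = 44240/1048576 = 4.2%.

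**Maximum true error by full enumeration.**

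| Arms | Pooled t | Welch t | Fisher |
|---|---|---|---|
| 8 v 8 | 7.7% | 7.7% | 2.1% |
| 9 v 10 | 6.5% | 6.4% | 2.1% |
| 10 v 10 | 4.2% | 4.2% | 1.3% |
| 12 v 12 | 6.4% | 6.4% | 2.3% |
| 10 v 15 | 6.0% | 5.8% | 4.0% |
| 15 v 15 | 5.5% | 5.5% | 1.8% |

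At 9 v 9 the maximum is 5.7% pooled but 3.3% Welch; at 8 v 10 Welch reaches 4.8%.

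**Dependence on the rate.** At 8 v 8 the error is 0.5% at an incidence of 10%, 2.7% at 20%, 5.3% at 30% and 7.1% at 40%. At incidences of 10% or less the t-test was conservative (under 3%).

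**No p-value.** The chance that neither arm varies is (1 − p)^(n+m) plus negligible terms at low p. At 10 v 10 this is 0.95^20 = 36% at a 5% incidence, 0.9^20 = 12% at 10%, and 0.8^20 = 1.2% at 20%.

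**Does the conclusion change?**

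| Table | Welch p | Fisher p | Boschloo p |
|---|---|---|---|
| 10 v 10: 0 v 4 | 0.037 | 0.087 | 0.042 |
| 10 v 10: 1 v 6 | 0.020 | 0.057 | 0.023 |
| 10 v 10: 2 v 7 or 3 v 8 | 0.024 | 0.070 | 0.041 |
| 8 v 8: 1 v 5 | 0.043 | 0.119 | 0.053 |
| 8 v 8: 2 v 6 | 0.049 | 0.132 | 0.077 |

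Of the tables examined, only those at 8 v 8 are significant by t-test and not significant under both exact tests.

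**The case against.** The strongest reply is that the t-test is valid at the planned size. At 10 v 10 its error never exceeds 4.2%, several neighbouring sizes are also safe in the Welch form, and 7.7% is the highest of the sizes tried, at the least favourable rate. All of that stands, and it limits the point to some sizes and mainly mid-range rates. It does not remove it, because 10 per group is fixed by a day 1 measurement. A single loss gives 9 v 10, where the maximum is 6.4-6.5%.

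A reader might infer from the Fisher p-values that a significant t-test at 10 v 10 would lack exact support. The figures do not bear this out. Boschloo's test, which is exact, gives p = 0.023-0.042 for all four of those tables, so the disagreement reflects Fisher's conservatism.

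A reader might also infer that an undefined t-test loses a finding. It does not in the case that matters: with no events in either arm no test would show a difference, and Fisher's returns p = 1. What is missing is a stated way to report that result.

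Two further replies have force. The outcome list in section 9 contains no yes/no measure, and incidence appears only in Hypothesis 2c without a cut-off; that definition is a more basic gap and belongs in the fix. The plan also provides for multiple imputation, so the fix must say how an exact test fits with it.

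**Conclusion.** The point holds as a minor correction. The written rule applies a t-test to a binary secondary outcome. At 10 v 10 this does no harm to the error rate. At some other attainable sizes the maximum error is 0.5 to 2.7 percentage points above the nominal 5% (5.5% at 15 v 15, 7.7% at 8 v 8), mainly at mid-range incidence. At low incidence the test is conservative but may return no p-value.

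The sizes and rates are assumptions, since the documents state neither retention nor expected incidence; that the rule has no exception for binary outcomes is plain from the text. The documents do not support reading this as general inflation of the secondary analyses, or as any flaw in the primary analysis or its sample size.

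**What to change.** In section 9, limit the t-test to continuous secondary outcomes. State that the incidence of chronic pain at 6 and at 12 months will be compared with one pre-specified exact test, preferably Boschloo's, which holds 5% by construction and is less conservative than Fisher's. Fisher's is acceptable and already named in the plan, but its maximum size is only about 1-3% at most of these arm sizes. Report the risk difference with a score-type confidence interval. Give the NRS cut-off, and say which NRS item it applies to. Add that the exact test uses observed cases, with any multiple-imputation analysis carried out on the risk difference.

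The cost is a few sentences and no extra data. A few borderline tables, such as 1 v 5 or 2 v 6 at 8 v 8, lose nominal significance; with Fisher's test the 10 v 10 tables shown above would lose it too.

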9. RESEARCH DESIGN AND METHODS

The cryoneurolysis procedure will be compared with our current UCSD standard practice.

Study Overview

Day 0

Baseline pain levels and spirometry

Subjects randomized and cryoneurolysis/sham procedure administered
Post-block pain levels and spirometry repeated

Days 1, 2, 7	Pain levels, opioid consumption, sleep disturbances due to pain, and incentive spirometry values collected [day of discharge recorded]
Months 0.5, 1, 1.5 , 2 3, 6, and 12	Pain levels, opioid consumption, sleep disturbances due to pain, and pain interference collected [if subject has spirometer available]

Subjects will be individuals who present to one of the UCSD hospitals with rib fracture(s) and significant pain. The University of Florida will be following the same protocol and the subjects from both institutions will be combined for the analysis. Those who consent to participate in this study will have standard ultrasound-guided intercostal nerve blocks administered with ropivacaine 0.5% (with epinephrine), 3 mL/level of each fracture rib as well as one level above and one level below.

Treatment group assignment (randomization). Subjects will be allocated to one of two possible treatments stratified by treatment center and unilateral vs. bilateral fractures:

1. **active cryoneurolysis (*sham local anesthetic intercostal blocks*)**
2. **sham cryoneurolysis (*active local anesthetic intercostal blocks*)**

Computer-generated randomization lists will be used to create sealed, opaque randomization envelopes with the treatment group assignment enclosed in each envelope labeled with the randomization number.

The specific intercostal nerves targeted will depend on the injury site. The treatment sites will be cleansed with chlorhexidine gluconate and isopropyl alcohol. Using the optimal ultrasound transducer for the specific anatomic location and subject anatomy (linear vs curvilinear array), the target nerves will be identified in a transverse cross-sectional (short axis) view. The intercostal nerve of each fractured rib as well as the level above and below will be treated with the protocol below:

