Intercostal nerve block procedure: The target nerve will be visualized with ultrasound. Local anesthetic (1% lidocaine) will be used to infiltrate the skin and underlying muscle at each entry point. A 20 g Tuohy needle will be introduced through the skin wheel and along the anesthetized muscle tract. For subjects randomized to active cryo, 3 mL of normal saline will be injected into the muscle superficial to the nerve; and for subjects randomized to sham cryo, 3 mL of ropivacaine 0.5% (with epinephrine) will be injected perineurally to provide the intercostal nerve block.

Cryoneurolysis procedure: Cryoneurolysis probes are available for a console neurolysis device (PainBlocker, Epimed, Farmers Branch, Texas) that either (1) pass nitrous oxide to the tip inducing freezing temperatures; or, (2) vent the nitrous oxide at the base of the probe so that no gas reaches the probe tip, resulting in no temperature change. The latter is a sham procedure since without the temperature change, no ice ball forms and therefore the target nerve is not affected. An angiocatheter/introducer will be inserted beneath the ultrasound transducer and directed until the probe tip is immediately adjacent to the target nerve. The angiocatheter needle will be removed, leaving the angiocatheter through which the appropriate Epimed probe will be inserted until it is adjacent to the target nerve. The cryoneurolysis device will be triggered using 2 cycles of 2-minute gas activation (active or sham) separated by 1-minute defrost periods. For active probes, the nitrous oxide will be deployed to the tip where a drop in temperature to -70°C will result in cryoneurolysis. For the sham probes, the nitrous oxide will be vented prior to reaching the probe shaft, resulting in a lack of perineural temperature change.

The process will be repeated with the same treatment probe for any additional nerves (e.g., all nerves will receive either active cryoneurolysis or sham/placebo, and not a mix of the two possible treatments).

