For subjects at the University of Florida, their anthropomorphic, baseline, procedure, and post-procedure data will be recorded on the same case report form as at the University California San Diego and faxed to the investigators at UC San Diego following the procedure. These faxed documents will remain in electronic form (eFax) on the Principal Investigator's password-protected, encrypted, UCSD-owned MacBook computer. Investigators at UC San Diego will do all of the follow-up data collection by phone for subjects at both treatment centers.

Outcome measurements (end points). Anesthesia providers will perform all measures and assessments, which will include:

1. **Pain:** measured on the 11-point NRS of pain intensity
2. **Opioid consumption**
3. **Pain interference:** measured using the Brief Pain Inventory (which includes the pain scores of #1 above)
4. **Sleep disturbances (#):** due to pain
5. **Pulmonary Mechanics:** measured by the inspired volume on a handheld incentive spirometer based on the American Association of Respiratory Care (AARC) clinical practice guideline.⁷ The best of three measurements will be recorded as the maximum inspired volume.

Statistical Analysis: The primary endpoint is the maximum inspired volume measured by incentive spirometry the day following treatment. There is no accepted minimal clinically-relevant change in incentive spirometry volume. However, the median (IQR) of inspired volume for patients with rib fracture(s) is 1250 (750-1750) mL,⁸ and, ISV<1000 mL is associated with an increased risk of acute respiratory failure.⁸ We will therefore use the difference between 1250 and 1000 (250 mL) as the minimal clinically-relevant difference. However, there is high variability in the reported increase in inspired volume with various regional analgesic interventions such as continuous intercostal nerve blocks⁹ and serratus plane blocks,¹⁰ and we will therefore increase our enrollment to account for an unpredicted increase in variability or non-normal data distribution.

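### The sensitivity analysis names the Wilcoxon signed-rank test, which needs pairs, but the two arms are independent; the rank-sum (Mann-Whitney) test should be named

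*Combined protocol and SAP*

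**What the plan says.** All of the relevant text is in section 9, Research Design and Methods, of the combined protocol and SAP.

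- **Primary comparison** (maximum inspired volume on the day after treatment): "The group difference will be tested using Welch's two-sample test".
- **Secondary outcomes:** "Secondary outcomes will also be tested with the two-sample t-test".
- **Sensitivity analysis:** after a sentence declining multiplicity adjustment, "The Wilcoxon signed-rank test will be used as a sensitivity analysis". The sentence does not say which outcomes it covers.
- **Randomization:** "Subjects will be allocated to one of two possible treatments stratified by treatment center and unilateral vs. bilateral fractures".
- **Cryoneurolysis procedure:** "all nerves will receive either active cryoneurolysis or sham/placebo, and not a mix of the two possible treatments".
- **Sample size:** "we will enroll 10 subjects per group with an evaluable primary outcome measure".

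**The concern.** The signed-rank test takes a single set of differences, either within pairs or from a fixed value. It does not compare two independent samples. The sentence follows two such comparisons and appears to be meant as their check, but a signed-rank test cannot serve as one in this design.

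The plan names no other rank-based test. Fisher's test is assigned to categorical baseline variables, and the repeated-measures model and ANCOVA compare means. The Statistical Analysis text gives possible non-normality as a reason for raising enrolment, so the authors had the issue in mind. Some of the outcomes to be t-tested are coarse: pain is "measured on the 11-point NRS of pain intensity", and sleep disturbance is a count. With 10 subjects per arm, a rank-based check is useful for such outcomes. If the wording stays, the analyst must decide after the data are in what was meant, and the check is no longer pre-specified.

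**Working it through.** **1. Does the design supply pairs?** Section 9 offers three possible sources.

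| Possible source of pairs | What section 9 describes | Pairs? |
|---|---|---|
| Between subjects | Individual allocation within strata of center and laterality | No: a stratum is not a matched pair |
| Within a subject, across nerves | One treatment at all nerves | No |
| Within a subject, over time | Baseline and follow-up values are collected, but no within-arm test is planned; change from baseline is handled by ANCOVA with group as a covariate | Not for the group comparison |

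**2. Does the sample size assume independent groups?** Inputs from Statistical Analysis: difference 250 mL, SD 200/1.35 = 148 mL, two-sided 5%, power 80%.

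- Standardized difference: 250/148 = 1.689.
- The independent two-sample t-test (noncentral t) gives n = 6.61, so 7 per group. Power is 75.1% at 6 and 82.6% at 7.

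The plan's 7 per group is reproduced, and it comes from an unpaired calculation.

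**3. What happens if the signed-rank test is forced onto the two arms?** The analyst has to invent a pairing. In one simulated data set of 10 against 10, 5,000 arbitrary pairings of the same values gave signed-rank p-values from 0.002 to 0.77. The rank-sum test gave a single p-value, 0.19. The signed-rank result therefore depends on the pairing chosen. If the evaluable groups differ in size, some subjects would also have to be left out.

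**4. What does the correct test cost relative to Welch?** The comparison is the exact two-sided rank-sum test against Welch's test, with 10 per group, normal data with equal SDs, alpha 0.05 and 200,000 replicates per setting. With 10 per group the exact test rejects when U ≤ 23 or U ≥ 77, which gives a size of 0.0433 from the null distribution of U.

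| True difference | SD | Rank-sum | Welch | Check: equal-variance t, noncentral t |
|---|---|---|---|---|
| 0 | 148 mL | 4.4% | 4.9% | – |
| 250 mL | 148 mL | 92.3% | 94.4% | 94.6% |
| 250 mL | 741 mL | 9.6% | 10.8% | 11.0% |

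The last row uses the interquartile range for inspired volume quoted in the same section, with the plan's own divisor: (1750 − 750)/1.35 = 741 mL. It is there only to show that the gap between the two tests stays small when the SD is larger: 94.4 − 92.3 = 2.1 points at 148 mL, and 10.8 − 9.6 = 1.2 points at 741 mL. Whether the trial is adequately powered is a separate question.

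**The case against.** The strongest reply is that everyone will read this as rank-sum. The sentence follows two two-sample tests, the signed-rank test cannot be run on unpaired arms without inventing pairs, and the likely outcome is that the analyst uses rank-sum. No decision rule depends on the sensitivity analysis, so a minor grade could be defended. The reading is probably right, but nothing in the documents confirms it, and a pre-specified test should not have to be inferred.

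A second reply is that the sentence might mean a within-arm test of change from baseline. That is technically possible, but no such analysis is planned, and it would not check a difference between arms.

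Two objections to the supporting material do stand:

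- The power figures measure the cost of the correction, not the harm done by the slip. They also assume normal data, where a rank test is least needed.
- The 4.3% exact size assumes no ties. Pain scores and counts will produce ties, so that figure and the 92.3% do not carry over to those outcomes.

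It is also true that the scope of the sensitivity analysis is inferred from its position in the text, and that extending it explicitly to the secondary outcomes is a clarification rather than part of the error.

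**Conclusion.** The concern holds. The plan names a test for paired or one-sample data as the check on comparisons between independent, unmatched arms. As written, that analysis has no defined result. It is probably a naming slip, but it sits in the operative analysis text and nothing elsewhere corrects it.

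The effect is limited. The primary Welch test, the 7 per group from the power calculation and the 10 evaluable per group all stand. What is missing is a usable pre-specified rank-based check. The conclusion about the test follows from the design alone and needs no distributional assumption. Only the estimate of about 2 points of power lost relative to Welch rests on normal data, equal SDs, 250 mL, 148 mL and 10 per group. It should be fixed before the data are analyzed.

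**What to change.** In section 9, Statistical Analysis, replace signed-rank with rank-sum (Mann-Whitney). In the same line, state that it applies to the day-1 primary outcome and to the secondary outcomes tested with the two-sample t-test.

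The cost is one line of text. Sample size, primary test and data collection do not change.

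### Opioid consumption is tested by t-test and, by implication, by a normal-error mixed model aimed at Month 12; a rank-sum lead analysis suits it better, and the rank test named is the paired one

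*Combined protocol and SAP*

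**What the plan says.** All of this is in section 9 unless stated.

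- **Outcomes.** The outcome list has five items. Two of them are opioid consumption and the number of sleep disturbances due to pain.
- **Schedule.** The Study Overview collects both on Days 1, 2 and 7. For the seven later contacts, Months 0.5 to 12, it lists "Pain levels, opioid consumption, sleep disturbances due to pain, and pain interference collected". That makes ten post-treatment contacts.
- **Test.** The Statistical Analysis text applies the two-sample t-test to the secondary outcomes and excepts none.
- **Model.** Secondary analyses include a mixed model for repeated measures with time, time-by-group, laterality and number of fractures. It treats time as categorical and "will assume a compound symmetric correlation and heterogeneous variance with respect to time". Its target is stated: "The estimated mean difference between groups at the final scheduled timepoint will be the parameter of interest". No outcome is assigned to it by name. Outcomes with a single follow-up go to ANCOVA.
- **Rank test.** The Wilcoxon signed-rank test is listed, as a sensitivity analysis only.
- **Size.** "we will enroll 10 subjects per group with an evaluable primary outcome measure (n=20 for both groups combined"), with a maximum enrolment of 30.

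There is no count, two-part or transformed analysis, and no rule for a visit at which an outcome does not vary.

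**The concern.** Opioid consumption cannot go below zero and is usually right-skewed. In this trial it is also likely to be zero for many subjects late on. Section 10 excludes chronic opioid users and patients with other moderate or severe pain. Section 7 expects the nerve block to last 6-8 weeks, and section 14 puts fracture healing at about 2 months. The model's target is Month 12.

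Two things follow. At the earlier contacts, a comparison of means in 10 subjects per arm is inefficient for skewed amounts, so an opioid-sparing effect is more likely to be missed. At the late contacts, a model with its own variance for each visit cannot be fitted if nobody varies at one of them. The rank test that might serve as a back-up is named in its paired form.

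**Working it through.** **Step 1. The plan's own figure.** The documents give no power or distribution for opioid consumption or sleep disturbances. The one stated calculation is for inspired volume. Its inputs are a difference of 250 mL, an SD of 148 mL and a 5% two-sided error rate, and its result is that "a sample size of n=7 per group provides 80% power". The standardised difference is 250/148 = 1.69. The noncentral t gives 6.61 per group, rounded up to 7, with power 0.826 at n = 7. The figure reproduces, and nothing below affects it.

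**Step 2. Chance that every subject is zero at a visit.** If a proportion q still uses opioids, P(all zero) = (1 − q)^n and P(at most one user) = (1 − q)^n + nq(1 − q)^(n−1). The documents give no q, so a range is assumed.

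| q | all zero, n = 20 | at most one user, n = 20 | all zero, n = 30 |
|---|---|---|---|
| 2% | 67% | 94% | 55% |
| 5% | 36% | 74% | 21% |
| 10% | 12% | 39% | 4% |
| 20% | 1% | 7% | 0.1% |

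**Step 3. What the model does then.** The specified model was evaluated on simulated data: 20 subjects, 10 visits, the stated fixed effects, and heterogeneous compound symmetry.

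- With all values zero at the last visit, each tenfold cut in that visit's SD raises the REML log-likelihood by (20 − 4) × ln 10 = 36.8. The 4 counts that visit's mean and group effect plus the two covariates. There is no maximum.
- When a floor was set for the SD, the fit always ended on it. As the floor went from 0.01 to 0.000001, the standard error of the final-visit difference fell from 0.0046 to 0.00000046.
- The covariates are not crossed with time, so the fracture-count coefficient was driven to zero for every visit.
- With one non-zero value the fit has a solution (last-visit SD 1.15), but it says little. If one subject of 20 reports an amount x, the two-sample difference is x/10. That arm's variance is (x² − x²/10)/9 = x²/10, so the standard error is √(x²/100) = x/10 and t = 1 whatever x is.

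**Step 4. t-test against rank-sum test for opioid amounts.** Simulated, 10 per arm, two-sided 5%. All distributions are assumed. The t-test is the pooled version; Welch's version rejected less often in each row.

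| Lognormal amounts | t-test | rank-sum |
|---|---|---|
| no zeros, median ratio 0.5, log-SD 0.8 | 34% | 40% |
| no zeros, ratio 0.4, log-SD 1.0 | 31% | 44% |
| 30% vs 70% zeros, ratio 0.5, log-SD 0.8 | 47% | 53% |
| same, log-SD 1.0 | 36% | 51% |
| same, log-SD 1.3 | 23% | 47% |
| 50% vs 20% users, same amount, log-SD 1.0 | 13% | 25% |

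The gap is roughly 5 to 25 points. With 70% zeros in both arms and no effect, the t-test rejects in 1.4% to 3.0% of trials: it is conservative, not invalid.

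**Step 5. Sleep-disturbance counts.** Negative binomial with dispersion k, pooled t-test against rank-sum, 10 per arm:

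- means 2 vs 0.5, k = 1: 42% vs 42%
- means 2 vs 0.5, k = 5: 73% vs 70%
- means 3 vs 1, k = 1: 35% vs 34%
- means 1 vs 0.1, k = 0.5: 30% vs 41%

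With Welch's version a separate run gave 36/42, 71/71, 31/34 and 22/41. The picture is mixed.

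**The case against.** The strongest reply has four parts.

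- **Coverage is inferred.** The plan never says that the mixed model is for opioid consumption or sleep counts. This stands. A reader might take coverage as fact; the text supports it only by elimination, because ANCOVA takes the single-follow-up outcomes. The silence is itself worth correcting.
- **Failure is conditional.** Every subject in both arms must be zero, and the rate is assumed. One non-zero value restores a solution. The t-test remains the stated test for secondary outcomes, and an analyst would probably drop an empty visit and refit. This stands too: what is missing is a pre-specified rule, and no outcome is left wholly unanalysed. The t-test does not rescue Month 12, however. With all zeros it is undefined, and with one user its value is fixed at 1.
- **A rank test is already planned, and non-normality is foreseen.** A reader might infer both. The test named is the signed-rank test, which needs paired data. The remark about a non-normal distribution concerns inspired volume and serves to justify enrolment. Neither covers opioid amounts.
- **The outcomes are minor.** No hypothesis in section 6 concerns opioids or sleep, and section 17 mentions less opioid use only as something that might follow. The point bears on secondary outcomes without multiplicity control, and neither test has high power at 10 per arm.

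**Conclusion.** The point holds for opioid consumption. Under assumed skewed amounts at 10 per arm, the planned t-test loses roughly 5 to 25 points of power against the rank-sum test. If the mixed model is applied as its wording implies, it has no REML solution when all subjects are zero at a visit. For 20 subjects that has a chance of 1% to 67% if 20% to 2% still use opioids, again an assumption. The signed-rank test is the wrong test for comparing two arms, and that needs no assumption.

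A reader might go further and say that the t-test wastes power for sleep disturbances as well. That is not shown: the pooled t-test equals or slightly beats the rank-sum test in three of the four scenarios tried. Nor is there evidence of false-positive inflation. The primary endpoint and its Welch test are unaffected.

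**What to change.** 1. Make the two-sample Wilcoxon rank-sum test the lead analysis of opioid consumption at each contact. Report medians (IQR), the proportion with any use in each arm and, where informative, a Hodges-Lehmann shift with 95% CI. The shift should not be the only estimate: with 50% vs 20% users it was exactly 0 in about 60% of simulated trials. Keep means and the t-test as supportive.
2. Replace signed-rank by rank-sum for the between-group sensitivity analysis, including for sleep disturbances.
3. Name the outcomes that the mixed model covers, and leave out opioid consumption and sleep-disturbance counts. For any outcome kept in it, drop visits with no variation and report them descriptively. Pain and pain interference can also reach zero, so the rule is needed there.

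A switch to Fisher's exact test on any versus no use from Month 3 is tempting but should not be made. For 20% vs 5% users its power was 2% against 8% for rank-sum, and for 30% vs 5% it was 10% against 23%.

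The cost is SAP wording only. The small downside is that the lead opioid result becomes a rank comparison without adjustment for laterality or number of fractures, and not a difference in means.
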